#### **7.1.1. Assessments in the Screening Period**

Patients will be evaluated for entry criteria during the Screening Period within 28 days before the first infusion of study drug. The following procedures and evaluations need to be completed for each patient before Day 1:

1. A written, signed-and-dated informed consent should be obtained before any screening procedures and receiving study drugs.

2. Inclusion and exclusion criteria are cross-checked.
3. Demographics and medical history (to include collection of prior medications administered to the patient during the Screening Period, prior and concurrent medical conditions, and baseline signs and symptoms)
4. Diagnosis confirmation and stage
5. History of tumor-specific therapy including chemotherapy and radiotherapy or any other forms of therapy.
6. ECOG performance status
7. Vital signs (temperature, pulse, respiratory rate and blood pressure), weight and height.
8. Physical examination including an elective neurological examination.
9. Documentation of disease assessment
10. Baseline condition assessment (record the amount of hemoptysis, if present).
11. Documentation of measurable diseases.
12. Review of pathology reports including mutation status
13. Complete blood count (CBC) with differentials and D-dimer.
14. Coagulation profile: prothrombin time, partial thromboplastin time, international normalized ratio (PT/INR/PTT).
15. Blood chemistry profile: Fasting glucose, blood urea nitrogen (BUN), creatinine, ALT, AST, total protein, albumin, globulin, alkaline phosphatase, total bilirubin, sodium, potassium, chloride, calcium, magnesium, phosphorus, uric acid, lactate dehydrogenase (LDH), IgG and IgM.
16. Lipid profile: total cholesterol, triglyceride.
17. Thyroid function tests: thyroid-stimulating hormone (TSH), T3, free thyroxine (FT4)
18. Serum lipase and amylase.
19. Hepatitis B surface antigen (HBsAg), hepatitis B core antibody (HBcAb), Hepatitis C antibody (anti-HCV).
20. Tumor markers (CEA, CA199, CA125, CA153, alpha-fetoprotein and PSA)
21. Serum βHCG test for female patients with child-bearing potential.

---

 Baseline signs and symptoms: Clinical adverse events occurring after signing informed consent, but before study drug administration are to be recorded on the Medical History/Current Medical Conditions CRF

 If all patients should have confirmed pathologic diagnosis, if not, a pathology review might be necessary.

 If no prior record of pathologic diagnosis is available, a tumor biopsy is required.

 PSA is needed for patients with prostate cancer.

 Postmenopausal women must be amenorrheic for at least 12 months in order not to be considered of child-bearing potential.

22. Urinalysis.
23. Chest radiograph (X-ray)
24. 12-lead electrocardiogram (ECG).
25. Tumor imaging with contrasted computerized tomography or MRI (chest, abdomen and pelvis) for tumor assessment (if the imaging studies are less than 6 weeks before 1st infusion of IP, no need to repeat the studies).
26. Contrast brain CT/MRI (if the imaging studies are less than 8 weeks before 1st infusion of HLX06, no need to repeat the test).
27. Cardiac ultrasound or a MUGA scan
28. Bone scan (if signs or symptoms suggestive of bone metastases are present).  
Confirmative X-ray, CT or MRI for bone metastases for patients with positive bone scan. *The selection of imaging modality is based on the discretion of investigators for the benefit of patients.*
29. Concomitant medications including alternative medicines.
30. Assessment of adverse events from prior therapies.

## 7.2. Treatment period

The treatment of the study is divided in cycles with associated evaluation and procedures that must be performed at specific time points. Subjects who meet inclusion/exclusion criteria may start the Investigation Product (IP) treatment within 28 days of Screening period. Each cycle of treatment is FOUR weeks. Enrolled patients will receive FOUR weekly infusions of IP in a cycle.

Following cycle 1, the decision whether to treat the patients with additional cycles of IP and which dose level to use in the next cycle will be determined by the toxicities of the prior cycle (refer to Section 7.2.2.1).

A patient who is withdrawn from the study before the completion of the first cycle for a reason other than treatment-emergent toxicities will be replaced.

---

 Urinalysis includes: color, turbidity, specific gravity, pH, leukocyte, nitrite, protein, glucose, ketones, urobilinogen, bilirubin, blood cells. If the urinalysis indicates significant proteinuria ( $> 30$  mg or  $>= 2+$  by urine dipstick), urinalysis must be repeated. If the repeat dipstick protein value is  $>30$  mg or  $>= 2+$  by urine dipstick, 24-hour urine collection is required to calculate total protein.

### **7.2.1. Interval of the first infusion between new patients in a cohort**

The interval of the first infusion between NEW patients in a cohort is **24** hours or longer, regardless of the dose level. This is to ensure the safety of patients in a cohort, in case there were excessive toxicities.

### **7.2.2. The requirement of hospitalization for the infusion of IP**

The Investigator may hospitalize the patients for the first infusion of IP and the PK/PD studies in cycle 1. Based on the reactions during and after the first infusion in cycle 1, it is up to the Investigator to determine whether extended hospitalization for observation and PK/PD studies are necessary. It is also the Investigator's discretion to determine whether hospitalization is needed for subsequent infusions.

#### **7.2.2.1. Determination of the dose level for the first infusion in a cycle**

This study adopts an adaptive trial design, which is different from conventional 3+3 design. Please refer to Section 3 for the detail of study design.

**In the accelerated phase, Investigators and the study staff need to assess the toxicities in the first cycle and communicate with the Study Monitor or its designee the dose level before the first infusion in the next NEW patient.**

#### **7.2.2.2. Pre-medications for the first and subsequent infusions in a cycle**

Primary prophylaxis for first infusion reaction of HLX06 is **NOT** mandatory. If the patients experience infusion reactions, allergic reactions, nausea, vomiting or other symptoms/signs related to infusion of experimental drugs, pre-medications to mitigate these reactions with antihistamine, acetaminophen, corticosteroid or 5-HT3 antagonist are permitted in subsequent infusions. Investigators could also follow institutional guidelines for pre-medications for infusion-related conditions.

#### **7.2.2.3. Procedures for the first infusion in a cycle.**

For preparation of IP and the requirement for infusion set, please refer to Section 5.6.

Treatment will begin with the first intravenous infusion of IP (Day 1) and will continue every 7 days for a total of 4 doses (Days 1, 8, 15 and 22) in a cycle with the response assessment described in Section 8.

The followings are the procedure required before the first infusion in each cycle: (*the laboratory tests before the first infusion may be waived, if the interval between screening tests and first infusion is less than 7 days, and the Investigator judges that the patient's condition remains stationary*).

1. Vital sign measurements to include temperature, pulse, and blood pressure will be obtained as defined in the Section 14.
2. Weight
3. Physical examination (including measurement of vital signs as well as pulmonary, heart, abdomen, and skin assessments with selective neurological examination)
4. ECOG performance status
5. 12-lead ECG
6. Complete blood count (CBC) with differentials, and D-dimer
7. Tumor markers (CEA, CA199, CA125, CA153, alpha-fetoprotein and PSA)
8. Coagulation profile: prothrombin time, partial thromboplastin time, international normalized ratio (PT/PTT/INR).
9. Blood chemistry profile: Fasting glucose, blood urea nitrogen (BUN), creatinine, ALT, AST, total protein, albumin, globulin, alkaline phosphatase, total bilirubin, sodium, potassium, chloride, calcium, magnesium, phosphorus, uric acid, lactate dehydrogenase (LDH), IgG, and IgM
10. Thyroid function tests: thyroid-stimulating hormone (TSH), T3, free thyroxine (FT4)
11. Urinalysis.
12. Urine pregnancy test for female patients with child-bearing potential..
13. Infusions of IP (after all other evaluations for the visit according to the Time and Events Table have been completed except for the post-infusion pharmacokinetic samples)

---

 ECG must be done predose and within 30 minutes after the end of 1st infusion.

 If the tests have been done during the Screening period, no need to repeat the tests before 1st infusion in cycle 1. These should be done every 8 weeks in the first 24 weeks and every 12 weeks thereafter.

For prostate cancer only.

 Lab data must be performed and reviewed before dosing. Any new Grade  $\geq 3$  laboratory abnormality, such as liver function test elevations, electrolyte fluctuation, or hematologic deterioration should be assessed for potential risk before dosing. In the event of uncertainty, the Medical Monitor should be contacted.

 If thyroid function tests have been performed in the Screening period, no need to repeat before the first infusion in cycle 1, but repeat the thyroid function tests every 8 weeks before the first 24 weeks and every 12 weeks after 24 weeks.

 In the screening period, serum pregnancy test is used. Before the first infusion, urine pregnancy is used. A positive urine pregnancy test must be verified by a serum  $\beta$ HCG test. Postmenopausal women must be amenorrheic for at least 12 months in order not to be considered of child-bearing potential.

14. Assessment of adverse events
15. Obtaining serum samples for pharmacokinetics as outlined in Section 9 (post-infusion samples should be drawn from a site other than the infusion site [i.e., contralateral arm] on infusion days.)
16. Obtaining serum samples for pharmacodynamics 
17. Obtaining serum samples for immunogenicity (collected before infusions)

Following Cycle 1, patients may receive additional cycles of therapy until disease progression, up to a maximum of one year, withdrawal from study or death, whichever occurs first. If the patient's disease remains stable and the patient is deemed to benefit from continuous treatment of IP, additional treatment beyond one year will be evaluated on a case-by-case basis and arranged between the Investigator and the Sponsor.

The evaluations performed for the first infusion in subsequent cycles are the same (except for the PK/PD studies) and the results will be recorded on the CRF. Details are tabulated in Section 14.

#### **7.2.2.4. Management for the infusion-related reactions**

For patients who experience first infusion reactions, please refer to Section 6.4 for the procedure and management.

#### **7.2.3. Procedures for subsequent infusions in a cycle**

Following the first infusion in a cycle, patients may receive additional infusions on day 8, 15 and 22 to complete the cycle of treatment. The maximum duration of IP to be administered to an individual patient in this study is one year.

The evaluations performed for the second to fourth infusion in a cycle are as follows:

1. Vital sign measurements to include temperature, pulse, and blood pressure will be obtained as defined in the Section 14.
2. Weight
3. Elective physical examination (including measurement of vital signs as well as pulmonary, heart, abdomen, and skin assessments)

---

 Detailed pharmacokinetic studies are conducted in the first week in Cycle 1 only.

 The samples are collected before and after one hour of first infusion in Cycle 1. Please refer to Section 9 for detailed time points.

4. ECOG performance status
5. Clinical laboratory tests (local and central laboratories) (Note: Lab data must be performed and reviewed before dosing)
6. Complete blood count (CBC) with differentials and D-dimer
7. Blood chemistry profile: fasting glucose, BUN, creatinine, alkaline phosphatase, ALT, AST, total bilirubin, total protein, albumin, globulin, sodium, potassium, chloride, calcium, magnesium, phosphorus, uric acid, lactate dehydrogenase.
8. Urinalysis.
9. Serum sampling for pharmacokinetic studies (*for first cycle only*)
10. Infusion of IP
11. AE assessment

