### **The definitions of DLT include:**

- Grade-4 nonhematologic toxicities;
- Grade $\geq$ 3 febrile neutropenia;
- Any grade-3 non-hematologic toxicities lasting more than 3 days despite of optimal supportive care;
- Grade-3 nonhematologic laboratory abnormalities that persist more than one week and require medical intervention or hospitalization;
- Grade-4 thrombocytopenia requiring platelet transfusion or leading to life-threatening bleeding event.
- Grade-4 neutropenia  $>$  7 days.

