### **1.3. Potential Risk and Benefits**

#### **1.3.1. Known potential risks**

HLX06 has not been tested in human before and its potential toxicities are unknown. Based on the nonclinical studies, HLX06 reacts with human and monkey VEGFR2, but not murine VEGFR2, so its prediction of toxicities in human is based on the monkey study with limited numbers. However, HLX06 is not the first monoclonal antibody targeting VEGFR2 to go into humans. Ramucirumab, a VEGFR-2 monoclonal antibody, has been widely used in different cancers with more than 1000 patients. When ramucirumab is used alone in a patient population similar to this study, the most common toxicity is grade-3 hypertension.[10] No increased risk of bleeding, venous thrombosis, proteinuria, or gastrointestinal perforation occurred[9]. However, when ramucirumab is used in combination with cytotoxic agents, it has a different toxicity profile. In the study with paclitaxel, the most common grade-3 or higher toxicities are neutropenia, leucopenia, hypertension, fatigue and abdominal pain.[11] When ramucirumab is used with FOLFOX chemotherapy as first-line therapy for colorectal cancer patients, the most common grade-3 or higher toxicities are neutropenia, fatigue, and neuropathy[12]. Based on the same target and similar mode of action by HLX06 in cancer cells, we expect the toxicity profile is likely to be similar to those observed in ramucirumab monotherapy. Although ramucirumab appears to be more tolerable than bevacizumab, Investigators have to remain vigilant given that no prior safety data are available for HLX06.

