## **9. PHARMACOKINETIC AND PHARMACODYNAMIC EVALUATIONS**

### **9.1. Pharmacokinetic studies**

Pharmacokinetic study is mandatory for all patients in this study. Blood samples should be drawn from a site other than the infusion site (i.e., contralateral arm) on days of infusion. If the infusion was interrupted, the reason for interruption will also be documented on the CRF.

For pharmacokinetic analysis of HLX06, blood samples of 5 mL were drawn pre-dose (within one hour before first infusion), after the end of infusion (within 30 minutes) and at 2, 4, 8 ( $\pm 15$  minutes allowable) hours as well as at 24, 48, 96, and 168 hours after the end of 1st and 4th infusion in Cycle 1. Additional time points include pre-dose and after the end of 2nd and 3rd infusions (within 30 minutes) in Cycle 1. Thereafter, the serum levels of HLX06 will be measured before the first infusion of Cycle 2 to Cycle 6 or up to 24 weeks, whichever comes first; and on the day of follow-up visit 1, whenever possible.

Blood samples will be processed to collect serum and stored at -70 degrees Celsius. Serum samples will be analyzed for HLX06 by a validated ELISA method.

Non-compartmental pharmacokinetic analysis will be used to estimate the PK parameters. The following parameters are determined from the serum concentration data of HLX06: maximum serum concentration ( $C_{max}$ ), time to reach  $C_{max}$  ( $T_{max}$ ), elimination rate constant ( $\lambda_z$ ), elimination half-life ( $t_{1/2}$ ), area under the serum concentration-versus-time curve within one dosing interval ( $AUC_{0-\tau_{au}}$ ), area under the serum concentration-versus-time curve until infinity ( $AUC_{0-\infty}$ ), volume of distribution during terminal phase ( $V_z$ ), and at steady state ( $V_{ss}$ ), total body clearance from serum CL, and mean residence time (MRT).  $C_{max}$ , and  $T_{max}$  are taken directly from the plasma concentration curve, terminal half-life is determined from the terminal slope of the log-transformed plasma concentration curve using linear regression on terminal data points of the curve.

Concentrations below the lower limit of quantification, which are before the last quantifiable data point, are taken as zero for calculating the AUC. Pharmacokinetic results are presented only descriptively. No statistical tests are performed with pharmacokinetic parameters.

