## 14. SCHEDULE OF ASSESSMENTS

Procedure	Screening	Cycle1				Cycle 2~6				Cycle 7 and after				Follow-up period
		D1	D8	D15	D22	D1	D8	D15	D22	D1	D8	D15	D22	
Days		1	2	3	4	1	2	3	4	1	2	3	4	
Weeks	-4 to 0													
Informed consent	X													
Inclusion/exclusion criteria	X													
Medical history 	X													
Demographics	X													
Baseline conditions 	X													
Pathology review 	X													
AE assessment 	X	X	X	X	X	X	X	X	X	X	X	X	X	X
Concomitant medications	X	X	X	X	X	X	X	X	X	X	X	X	X	x
DLT evaluation 		X	X	X	X									
Efficacy assessment 		Assess every 8 weeks in the first 24 weeks and every 12 weeks thereafter												

 Medical history includes collection of prior medications administered to the patient during the Screening Period, prior and concurrent medical conditions, baseline signs and symptoms.

 Baseline condition includes vital signs, performance status, adverse events left from prior therapies, amount of hemoptysis.

 Pathology review includes confirmation of pathology, its mutation status AE assessment includes the adverse events left from prior therapies, the AE occurs after signing informed consent, but before the 1st infusion of IP.

 AE assessment includes the adverse events left from prior therapies, the AE occurs after signing informed consent, but before the 1st infusion of IP.

 DLT defining period is the first 4 weeks after the start of treatment.

 Efficacy assessment is done every 8 weeks in the first 24 weeks, every 12 weeks thereafter.

Procedure	Screening	Cycle1				Cycle 2~6				Cycle 7 and after				Follow-up period
Days		D1	D8	D15	D22	D1	D8	D15	D22	D1	D8	D15	D22	
Weeks	-4 to 0	1	2	3	4	1	2	3	4	1	2	3	4	
Survival status 														X
Treatment/Drug Administration														
Hospitalization for infusion and PK study		X			X									
HLX06 infusion		X	X	X	X	X	X	X	X	X	X	X	X	
Clinical procedures														
Vital signs/weight	X	X	X	X	X	X	X	X	X	X	X	X	X	X
Physical examination	X	X	X	X	X	X	X	X	X	X	X	X	X	X
Performance status assessment	X	X	X	X	X	X	X	X	X	X	X	X	X	X
Laboratory procedures														
CBC w/ DC and D-dimer	X	X	X	X	X	X	X	X	X	X	X	X	X	X
Blood chemistry 	X	X	X	X	X	X	X	X	X	X	X	X	X	X
Lipid profile 	X													
Urinalysis 	X	X	X	X	X	X	X	X	X	X	X	X	X	X

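### Cycle 1 blood pressure and laboratory values are scheduled weekly and no repeat interval is set, so duration-based DLTs without symptoms, above all grade-3 hypertension, cannot be reliably classified from scheduled data

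*Combined protocol and SAP*

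**What the plan says.** **DLT criteria (Synopsis).** Three of the six criteria contain a duration:
- "Any grade-3 non-hematologic toxicities lasting more than 3 days despite of optimal supportive care"
- grade-4 neutropenia lasting more than 7 days
- "Grade-3 nonhematologic laboratory abnormalities that persist more than one week and require medical intervention or hospitalization"

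The other three do not: grade-4 non-hematologic toxicity, febrile neutropenia of grade 3 or higher, and grade-4 thrombocytopenia with platelet transfusion or life-threatening bleeding.

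**Measurement schedule.** For infusions 2 to 4, Section 7.2.3 states "Vital sign measurements to include temperature, pulse, and blood pressure will be obtained as defined in the Section 14". In Section 14 the row "Vital signs/weight" has one mark at each of Days 1, 8, 15 and 22 of Cycle 1, as do the rows for blood count, chemistry and urinalysis. Laboratory tests precede dosing. At the first infusion of a cycle, Section 7.2.2.3 places the infusion "after all other evaluations for the visit according to the Time and Events Table have been completed except for the post-infusion pharmacokinetic samples". For infusions 2 to 4, no time of the blood pressure reading relative to the infusion is given.

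**Mid-week attendances.** Section 9.1 has PK blood drawn "as well as at 24, 48, 96, and 168 hours after the end of" infusions 1 and 4 of Cycle 1. No blood pressure reading is listed at those times.

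**Expected toxicity.** For ramucirumab alone in a similar population, Section 1.3.1 says "the most common toxicity is grade-3 hypertension" and expects HLX06 to behave similarly.

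**The concern.** High blood pressure, abnormal chemistry and low neutrophil counts often cause no symptoms, so their start and end are known only if somebody measures. Measurements seven days apart are too coarse for a limit of three days, and only just reach a limit of seven.

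DLT status decides a good deal. In the titration phase a cohort is one patient, and the next patient goes up a level unless that patient had a DLT, although a second grade 2 or higher toxicity also ends titration. After that, DLT counts drive Table 1 and the isotonic estimate of the MTD. If the same episode would be called a DLT at one site and not at another, depending on who rechecked and when, the count behind the primary endpoint is not well defined.

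**Working it through.** **Inputs.** Visit spacing is 7 days (Sections 7.2.2.3 and 14). The limits are more than 3 and more than 7 days (Synopsis). Assumption: episode onset is uniform within the week. The plan states no figure for ascertainment, so there is none to reproduce for this step.

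**1. Chance that an episode of L days falls between visits.** For L below 7 this is 1 - L/7.

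| L (days) | Not seen at any visit | Seen once |
|---|---|---|
| 3 | 57% | 43% |
| 4 | 43% | 57% |
| 5 | 29% | 71% |
| 6 | 14% | 86% |

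A 3-day episode (within the limit) and a 4-day episode (beyond it) look the same when each is seen once.

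**2. What k consecutive positive visits show.** The duration lies between 7(k-1) and 7(k+1) days, taking the finding as continuous between visits.
- One positive visit: 0 to 14 days. Neither limit is settled.
- Two positive visits: 7 to 21 days. The 3-day limit is settled. The 7-day limit is reached but not strictly exceeded.
- For L from 7 to 14, the chance of two positive visits is (L-7)/7: 14% at 8 days and 43% at 10 days.

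**3. Possible effect on the design (illustration).** The documents do not give the share of true DLTs that would go uncounted, so a range is shown. Simulated trials used the Table 1 boundaries, cohorts of 3, a maximum of 30 patients, a stop at 15 on one dose and isotonic selection. They started at level 1 or level 2, without the single-patient titration phase, with 20,000 trials per cell. The true rates were those of Table 2 scenario 1 (0.05, 0.10, 0.30, 0.45, 0.60, 0.80), and the observed rate was the true rate x (1 - share uncounted).

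Table 2 itself gives 58.5% correct selection and 20.0 + 2.3 + 0 = 22.3% selection of a dose with a true rate of 45% or more. The first row below is close to that.

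| Share uncounted | Correct MTD | Dose with true rate of 45% or more |
|---|---|---|
| 0 | 60-61% | 22-24% |
| 5% | 57-58% | 28-30% |
| 10% | 54-55% | 34-35% |
| 20% | 43-45% | 48-50% |

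For a single decision at n = 3, where Table 1 escalates on 0 DLTs, a true rate of 45% gives (1 - 0.45)^3 = 17% escalation. With 10% uncounted the figure is (1 - 0.405)^3 = 21%.

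**4. Effect of using the PK attendances.** Adding 24, 48 and 96 h to the weekly visits gives gaps of 1, 1, 2 and 3 days in weeks 1 and 4. No gap exceeds 3 days, so every 4-day episode in those weeks is seen at least once (100%, against 57%). Weeks 2 and 3 keep the 7-day gap.

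**The case against.** A reader might infer that the expected toxicities cannot be classified as DLTs at all. The documents do not support that. Three criteria have no duration, symptomatic events can be dated by history, and two consecutive positive visits settle the 3-day limit.

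A reader might also take the 43% as the share of 4-day DLTs that is lost. That goes too far as well. The 3-day criterion applies despite optimal supportive care, and the one-week laboratory criterion also needs intervention or hospitalization, so an episode nobody saw does not plainly meet either. Neutropenia is reported in Section 1.3.1 for ramucirumab with cytotoxic agents, not as an expected single-agent toxicity.

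The protocol does prompt extra checks:
- Section 6.4 calls close blood pressure monitoring crucial. Above 160 mmHg systolic or 100 mmHg diastolic, it has the dose reduced, or held while antihypertensive treatment is titrated.
- Section 10.1 requires start and end dates and follow-up to resolution or stabilization.
- Section 10.8 requires potential DLTs to be reported within 24 hours.
- Significant proteinuria triggers a repeat urinalysis.
- Section 14 marks hospitalization for infusion and PK on Days 1 and 22, and Section 7.2.2 allows a longer stay for observation.

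All of this stands, and it makes total loss of information unlikely. But none of these provisions sets a time to the next measurement or says how to count an undocumented duration. They allow good ascertainment without requiring it.

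Finally, it is tempting to say that escalation is pushed upward. That is not established, because a 3-day event counted as a DLT would push the other way.

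**Conclusion.** The point holds in a limited form. Scheduled data alone cannot reliably classify symptomless measured events under the duration-based criteria, and the protocol leaves the remainder to site practice. It matters most for grade-3 hypertension under the 3-day limit, because that is the toxicity the protocol cites first and the limit that weekly data resolve worst.

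The 43%, 29% and 14% rest on uniform onset and on scheduled visits only. They describe episodes not seen, not DLTs lost. The simulated effect is conditional on an assumed undercount and ignores over-counting, so it shows how sensitive MTD selection is and does not predict what will happen in this trial. This is a gap to close in a routine amendment. It does not invalidate the design.

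**What to change.** 1. In Section 14, 7.2.2.3 and 7.2.3, add a blood pressure reading at the existing Cycle 1 PK attendances 24, 48 and 96 h after infusions 1 and 4.
2. After any grade 3 or higher blood pressure or non-hematologic laboratory finding, or grade-4 neutropenia, in Cycle 1, require a repeat measurement at or before the duration limit that applies and, if not recovered, another just after it. The sponsor sets the exact interval. A repeat taken only after the limit would not do, since it cannot show recovery within it. This step also covers findings made in weeks 2 and 3; short episodes that fall wholly between visits in those weeks would still go unseen.
3. In Sections 6.1 and 11.1.1, pre-specify how an event is counted for Table 1 and the MTD when the repeat was not done.
4. Reconcile the two grade-3 criteria. A non-hematologic laboratory abnormality lasting 4 to 7 days meets the general 3-day criterion if read as a toxicity, but not the one-week laboratory criterion.

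The cost is a few blood pressure readings at visits already planned, plus routine repeat tests in patients with a qualifying finding. DLT counts become slightly conservative if missed repeats are counted as exceeding the limit.
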